4 CLINICAL PLAN SUMMARY

Up to 75 additional efficacy evaluable subjects (25 efficacy evaluable subjects per each of the 3 treatment arms) with submassive PE will be enrolled in the study at up to 20 clinical sites in the UK. Once a subject provides Informed Consent and receives treatment with EKOS, those data will be collected and analyzed. While all subjects who meet enrollment criteria will be treated, efficacy evaluable patients will include treatment with two catheters. (Note:There are two doses of r-tPA in each treatment group and the dose is determined by the number of catheters placed. All data will be summarized by total r-tPA dose administered, i.e. six groups; however, the primary analysis will be based on patients who have bilateral catheters placed.) It is anticipated that 30 subjects per treatment group will be enrolled to achieve 25 bilaterally treated efficacy evaluable subjects.

Additional subjects may be consented to compensate for screen failures, patients who are treated with one catheter and/or treated patients who lack sufficient data to be evaluable. The total number of consented patients will not exceed 120.

This is a randomized, parallel, multi-arm, multi-center study extended to continue investigating the optimal dose of r-tPA together with the optimal duration of ultrasound utilizing the EKOS device as a treatment for submassive PE. The study is planned to evaluate the reduction of right ventricular dysfunction and overall safety in three APT treatment groups. Subjects with submassive PE (hemodynamically stable PE with a RV/LV ratio ≥ 0.9 and at least one elevated biomarker) will be randomized to one of three APT treatment groups: ultrasound of 2 hours with r-tPA 2 mg/hr/catheter and ultrasound 4 and 6 hours with r-tPA, 1 mg/hr/catheter.

Treatment Group	Treatment Duration (hrs.)	Total Dose r-tPA (one/two catheters (mg)	r-tPA Infusion Rate
1	2	4/8	2 mg/hr/catheter
2	4	4/8	1 mg/hr/catheter
3	6	6/12	1 mg/hr/catheter

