10 STATISTICAL ANALYSIS

10.1 Analysis Subject Sets, Evaluable Subjects and Missing Data Handling Convention

Intent-to-Treat (ITT) Subject Set includes all randomized subjects; analyses performed on the ITT Subject Set will be by randomization treatment assignment regardless of actual treatment’s deviations from the assigned treatment protocol. Unless otherwise specified, all available data will be used for ITT analyses regardless of whether the assessment timing is within the pre-specified window.

Efficacy Evaluable Subject Set are defined as randomized subjects who met all eligibility criteria, received the randomization assigned APT Procedure with bilateral EkoSonic treatment, and for whom CTA imaging data are available and the assessments are within the pre-specified window at both Screening/Baseline (within 48 hours prior to APT start) and 48 ± 6 hours from the beginning of the APT procedure.

Safety Evaluable Subject Set are defined as randomized subjects for whom the APT Procedure was initiated, i.e. venous access attempted for EkoSonic catheter introduction. Safety analysis will be performed on the Safety Evaluable Subject Set according to the actual treatment received.

Missing data will not be imputed for the efficacy and safety analyses.

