Primary Safety Endpoint:	Major bleeding within 72 hours after initiating the APT Procedure																			
Population:	Subjects with acute symptomatic submassive PE with embolus located in at least one main or proximal lobar pulmonary artery and an end-diastole diameter RV/LV ratio ≥ 0.9 and at least one elevated biomarker. Subjects must be ≥ 18 to ≤ 75 years of age, have had PE symptoms for ≤ 14 days, and be able to be treated with APT Procedure within 48 hours of diagnostic CTA scan.																			
Treatment Arms:	
  
 Treatment Group	Treatment Duration (hrs.)	Total dose r-tPA (one/two catheters (mg))	r-tPA infusion Rate	
   
 1	2	4/8	2 mg/hr/catheter	
 
 2	4	4/8	1 mg/hr/catheter	
 
 3	6	6/12	1 mg/hr/catheter	
  
 
Please note that there are two doses of r-tPA in each treatment group and the dose is determined by the number of catheters placed. All data will be summarized by total r-tPA dose administered, i.e. six groups; however, the primary analysis will be based on patients who have bilateral catheters placed.
				Treatment Group	Treatment Duration (hrs.)	Total dose r-tPA (one/two catheters (mg))	r-tPA infusion Rate	1	2	4/8	2 mg/hr/catheter	2	4	4/8	1 mg/hr/catheter	3	6	6/12	1 mg/hr/catheter
Treatment Group	Treatment Duration (hrs.)	Total dose r-tPA (one/two catheters (mg))	r-tPA infusion Rate																	
1	2	4/8	2 mg/hr/catheter																	
2	4	4/8	1 mg/hr/catheter																	
3	6	6/12	1 mg/hr/catheter																	
Post-APT procedure Follow-up:	Within four hours of completion of the APT Procedure, the subject will be assessed for signs and symptoms of PE including a Pulmonary Embolism Severity Index (PESI/sPESI) and have an echocardiogram obtained. Additional echocardiograms will be obtained at 24 and 48 hours in addition to a CTA at 72 hours. The subject will return to the clinic at 30, 90 and 365 days for echocardiogram and QOL assessments.																			

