Enrollment:	
OPTALYSE PE 101 subjects were randomized and 100 treated in the OPTALYSE PE study and were followed for one year.
 
OPTALYSE PE – UK Extension (OPTALYSE UK) Up to 120 additional subjects were planned to be enrolled in the UK Extension study to obtain up to 75 efficacy evaluable subjects (25 efficacy evaluable subjects enrolled and randomized in each of 3 treatment arms.). Due to slow enrollment and the ability for sites to participate in the KNOCKOUT study, the OPTALYSE UK sites were instructed to stop enrollment on May 1, 2019. 29 subjects were enrolled in OPTALYSE UK and sites were instructed to continue following subjects for one 1 year per the protocol.
 
Evaluable subjects are those who have RV/LV assessments within specified windows and scores available at baseline and at 48 hours from the start of treatment.
																			

A. PROTOCOL SYNOPSIS

Clinical Sites:	
OPTALYSE PE 19 centers within the United States and the United Kingdom enrolled into OPTALYSE PE.
 
OPTALYSE PE – UK Extension (OPTALYSE UK) Up to 10 centers located in the United Kingdom were planned for OPTALYSE UK. At the time enrollment was stopped, 5 sites had enrolled subjects into OPTALYSE UK.

Time Course:	
OPTALYSE PE Enrollment into OPTALYSE PE took place from June 2015 through November 2016 with 1 year follow-up.
 
OPTALYSE PE – UK Extension (OPTALYSE UK) Enrollment into OPTALYSE UK took place from October 2017 through March 2019 with 1 year follow-up.

B. SCHEDULE OF ASSESSMENTS - OPTALYSE UK

	Screening/ Baseline ¹	Post APT Procedure				Follow-up - Clinic Visit			
	Day -2 within -48 Hrs. of APT start	Day 0 within 4 Hrs. of APT end	Day 1 24 Hrs. ±6 hrs of APT start	Day 2 48 Hrs. ±6 hrs of APT start	Day 3 72 Hrs. of APT start or D/C ¹⁰	Day 30 ± 5 D	Day 90 ± 10 D	Day 365 ± 14D	Early Term ¹¹
Informed Consent	X								
Demographics	X								
Medical History, Physical Exam, & Risk Factors	X								
Vital Signs ^{2,3}	X	X	X	X		X	X	X	X
Electrocardiogram	X								
CTA	X			X					
Hemodynamics/SvO ₂ ⁴	Optional								
PESI/sPESI	X	X	X	X					
Echocardiogram ^{5,6}	X	X	X	X		X	X	X	X
Laboratory Tests ⁷	X	X		X					
Biomarkers: Troponin, BNP/NT-proBNP, lactate/lactic acid, and D-dimer	X			X					
6 Minute Walk Test (6MW)						X	X	X	X
QOL Assessment: PEmb-QOL; EQ-5D- 5L						X	X	X	X
Adverse/VTE/Bleeding Events		X	X	X	X	X	X	X	X
Anticoagulant medications ⁸	X	X	X	X	X	X	X	X	X
Concomitant medications ⁹	X	X	X	X	X	X	X	X	X

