2 STATISTICAL ANALYSIS

2.1 Analysis Subject Sets and Missing Data Handling Convention

The **Intent-to-Treat (ITT) Subject Set** includes all randomized subjects; analyses will be performed for all primary and secondary efficacy endpoints for the ITT Subject Set. Unless otherwise specified, all available data will be used for ITT analyses regardless of whether the assessment timing is within the specified window.

The **Efficacy Evaluable (EE) Subject Set** includes randomized subjects who received the APT Procedure with EKOS treatment and for whom a CTA calculated RV/LV ratio is available at both baseline and 48 ± 6 hours from the beginning of the APT procedure. For the primary endpoint of CTA RV/LV ratio change from baseline to 48 ± 6 hours only, a subset analysis will be performed for EE patients in the ITT Subject Set. These analyses will only include data obtained in the pre-specified windows of (a) within 48 hours before APT start for baseline and (b) within ± 6 hours for 48 hours from APT start.

Safety Evaluable Subjects are defined as enrolled subjects for whom the APT Procedure was initiated, i.e. venous access attempted for EkoSonic catheter introduction, as indicated in database by a non-mising start time for EkoSonic placement (EXSTTM in the interventional procedure (EX) dataset). The **Safety Subject Set (SSS)** includes all safety evaluable subjects and will be used for all safety analyses.

Missing data will not be imputed for the efficacy and safety analyses.

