2.3 Efficacy Analyses

2.3.1 Primary Efficacy Analysis

The primary efficacy outcome is the change in the RV diameter-to-LV diameter ratio, from Screening/Baseline to 48 ± 6 hours after the start of the APT procedure, as determined by CTA. For each treatment arm, the mean RV/LV ratio change will be compared to the historical control value of a 0.20 reduction for the heparin arm¹. For this study, a 1-sided $p < 0.15$ by t test rejecting a ≤ 0.20 reduction will be regarded as a positive sign for further investigating a treatment regimen. As an example, should the standard deviation be 0.41 as observed in the SEATTLE II study, with 25 evaluable subjects the 1-sided p value would be <0.15 if the mean RV/LV ratio reduction is 0.29 or higher. To limit the 3-arm total false positive error rate to 0.15, the Hochberg procedure² will be used for statistical testing.

The main primary endpoint analyses will be performed for the ITT Subject Set and the Evaluable Subjects subset.

To explore a potential increasing trend in RV/LV ratio reduction for treatment Groups 1 through 3 as defined in Protocol Synopsis, i.e. Group 1 having the least reduction and Group 3 having the most reduction, an exploratory regression analysis will be performed on both absolute change and percent change data from all 3 groups. The independent variables will include baseline RV/LV ratio value, the unilateral vs. bilateral PE indicator, and treatment groups 1 through 3 coded ordinally as 1, 2, and 3. This exploratory analysis will only be performed on the ITT Subject Set.

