11) Core Lab RV/LV ratio from CTA: Baseline, 48 hours Post APT Start, absolute difference (Post-Procedure - Baseline) and percent change*

Summarize as continuous data for all above, i.e. n, mean, SD, median, minimum, maximum; provide 95% CI's for mean absolute and percent changes; provide 1-sided and 2-sided p values testing reduction ≤ 0.20 by t test for mean absolute change from baseline; provide same p values testing reduction ≤ 0 by t test for mean percent change from baseline.

All analyses above for RV/LV ratio by CTA will be repeated for the efficacy evaluable patient subset for ITT patients.

Lastly, repeat the above analyses for ITT patients as 6 arms, i.e. unilateral vs. bilateral for each of the 3 randomization arms.

Using continuous data from all 3 arms, perform increasing benefit trend analysis as described in the last paragraph of Section 2.3.1 and provide the 2-sided p value. (ITT only)

12) Core lab echocardiogram: Baseline, within 4 hours of APT end, 24 and 48 hours post APT start, Day 30, Day 90, Day 365 (procedure start date = Day 0) and change from baseline at all post-baseline time points (for continuous endpoints a-c below, besides summarizing as n, mean, SD, median, minimum and maximum at each of the 7 time points, also provide box-wisker plots for all time points on the same graph)*

- RV/LV ratio (perform same analysis at all time points as for the primary endpoint of RV/LV ratio as described in (11) above with the exceptions that testing a mean reduction of 0.20 applies to the 48 hours time point only and binary endpoint applies to \leq baseline vs. $>$ baseline only) (ITT)
- TAPSE (perform same analysis at all time points as for the primary endpoint of RV/LV ratio as described in (11) above, except mean absolute changes from baseline are tested against 0 as opposed to 0.20 and all p values are 2-sided and binary endpoint applies to \leq baseline vs. $>$ baseline only) (ITT)
- Estimated RVSP (perform same analysis at all time points as for the primary endpoint of RV/LV ratio as described in (11) above, except mean absolute changes from baseline are tested against 0 as opposed to 0.20 and all p values are 2-sided and binary endpoint applies to \leq baseline vs. $>$ baseline only) (ITT)
- IVC collapse with respiration (summarize as frequency and proportion at each time point and 2 \times 2 tables for changes from baseline, provide p values by McNemar's test) (ITT)

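### The SAP's Efficacy Evaluable set keeps the protocol's name but drops three of its conditions: eligibility, receipt of the assigned regimen, and bilateral treatment

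*SAP*

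**What the plan says.** Protocol 10.1 defines the Efficacy Evaluable Subject Set as "randomized subjects who met all eligibility criteria, received the randomization assigned APT Procedure with bilateral EkoSonic treatment", with in-window CTA data at baseline and 48 hours. Protocol 4 agrees on the catheter condition: "efficacy evaluable patients will include treatment with two catheters".

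SAP 2.1 uses the same name for a set that "includes randomized subjects who received the APT Procedure with EKOS treatment and for whom a CTA calculated RV/LV ratio is available" at baseline and 48 hours, with in-window data only. The Enrollment row of the SAP synopsis has a shorter sentence: "Evaluable subjects are those who have RV/LV assessments within specified windows and scores available at baseline and at 48 hours". The Treatment Arms row of the same synopsis nevertheless says that "the primary analysis will be based on patients who have bilateral catheters placed".

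SAP 2.3.1 gives the set its role: "The main primary endpoint analyses will be performed for the ITT Subject Set and the Evaluable Subjects subset". Appendix 1, item 11 adds: "All analyses above for RV/LV ratio by CTA will be repeated for the efficacy evaluable patient subset for ITT patients". That item carries the asterisk for the combined analysis, and SAP 2.2 says the pooled analysis uses the same subject sets.

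**The concern.** The trial's objective is to find the best combination of dose and duration. ITT already answers the as-randomised question. The protocol's evaluable set is the natural companion to it, because it shows what happened in eligible subjects who received the assigned bilateral regimen.

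Under the SAP the evaluable set differs from ITT mainly by receipt of some APT treatment, scan availability and scan timing. An ineligible subject, a subject given another arm's rate or duration, and a subject treated with one catheter (half the arm's two-catheter r-tPA dose) all count as evaluable in their randomised arm if their scans are in window. A reader who sees the protocol's term in a report will assume that Protocol 10.1 was applied.

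**Working it through.** **1. Conditions side by side**

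| Condition | Protocol 10.1 | SAP 2.1 | SAP synopsis, Enrollment |
|---|---|---|---|
| Met all eligibility criteria | yes | no | no |
| Received the assigned APT Procedure | yes | any APT with EKOS | not stated (window runs from start of treatment) |
| Bilateral treatment | yes | no | no |
| In-window CTA at both times | yes | yes | yes |

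**2. Does anything else in the SAP restore the conditions?**

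- SAP 2.3.1 and item 11 use the evaluable subset without further exclusions.
- Item 11 also says to "repeat the above analyses for ITT patients as 6 arms, i.e. unilateral vs. bilateral for each of the 3 randomization arms". This separates bilateral subjects, but only within ITT. It does not apply eligibility or the assigned regimen.
- Items 7d, 9 and 10 tabulate dose, infusion rate, infusion and ultrasound durations, termination reasons and deviations. Item 21 of the ITT list reports protocol deviations. None of these feeds an analysis set.

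**3. The plan's own power figure**

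Inputs (SAP 2.5): reduction 0.43, SD 0.41, null 0.20, one-sided alpha 0.15, n=25. The test is a one-sample t test, with power from the noncentral t distribution.

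- Noncentrality = (0.43 − 0.20) × √25 / 0.41 = 2.80. Power = 0.959, against 0.96 in the SAP and 0.95 in Protocol 10.5.
- All three arms under Hochberg, taken as independent: 0.959³ = 0.88, as the SAP states.
- Smallest reduction giving p<0.15: 0.20 + 1.059 × 0.41/√25 = 0.287, against the stated 0.29.

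The sample-size figures are therefore sound. The problem lies in who enters the set.

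**4. Illustration of size**

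Assumptions, none given in the documents: the 29 UK subjects split about evenly (29/3 ≈ 10 per arm); a share f of an arm falls outside the protocol definition; those subjects have mean reduction m; SD stays at 0.41. Arm mean if they are kept = (1 − f) × 0.43 + f × m. Enrolment is closed, so excluded subjects are not replaced, and the arm mean without them is 0.43.

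| f | m | Mean if kept | Power if kept, n=10 | Power if excluded |
|---|---|---|---|---|
| 0 | – | 0.430 | 0.753 | – |
| 10% | 0.20 | 0.407 | 0.695 | 0.722 (n=9) |
| 20% | 0.20 | 0.384 | 0.633 | 0.687 (n=8) |
| 20% | 0.30 | 0.404 | 0.687 | 0.687 (n=8) |
| 20% | 0.43 | 0.430 | 0.753 | 0.687 (n=8) |

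In the worst case shown, exclusion gains 0.687 − 0.633 = 0.05. The gain is nil at m of about 0.30 and becomes a loss above it.

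**The case against.** The strongest reply is that the looser set is defensible. The discontinuation events in Protocol 6.3.4 (vessel or cardiac injury, deterioration requiring CPR, neurological change) arise after randomisation and may be prognostic. Excluding those subjects can flatter a regimen tested against a fixed 0.20. ITT remains a main primary analysis, deviations will be tabulated, and the test is only a signal for further work. All of this stands. It is a reason to declare and justify the change, not to make it silently under the protocol's name. Protocol 10.2 leaves further analysis details to the SAP, but removing membership conditions from a protocol-defined set is more than detail.

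Several stronger readings are tempting, and the documents do not support them:

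- *Three competing definitions.* The synopsis sentence measures its window from the start of treatment, so it presupposes treatment and in practice picks out much the same subjects as SAP 2.1. The conflict is between protocol and SAP.
- *Every subject with a stopped infusion, or with infusion continued without ultrasound, is non-evaluable under the protocol.* Protocol 6.3.4 requires discontinuation after certain events, and 8.5.2 allows infusion without ultrasound after a malfunction. Protocol 10.1 does not say whether such subjects received the assigned procedure.
- *The looser set costs the drop from 0.75 to 0.63.* That comparison treats deviators as replaceable and assumes that all of them gain nothing beyond the heparin value. Protocol 1.2 reports suggested equipoise between the three arms, so a subject given another arm's regimen need not do worse.
- *The set was loosened for a purpose.* The SAP is dated after enrolment stopped, but the documents give no motive.

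**Conclusion.** The point holds as a discrepancy between protocol and SAP. All three conditions of Protocol 10.1 are missing from SAP 2.1, nothing elsewhere in the SAP restores them for the evaluable set, and the bilateral omission also contradicts the SAP's own synopsis. The set carries one of two main primary analyses and extends to the pooled data, so it should be corrected. This conclusion rests on the text alone.

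The size of any bias is unknown, because the documents give neither the share of subjects affected nor their response. The power figures of 0.63 (kept) and 0.69 (excluded) are a worst case under the assumptions listed above. Power is not the reason for the change. The reason is that the reported evaluable result should be the one the protocol names.

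**What to change.** 1. Make SAP 2.1 match Protocol 10.1 on all three conditions. Restoring only some of them would leave the same name on a different set. If the looser set is intended, give it another name, justify it, and report the protocol-defined set as well.
2. Replace the synopsis sentence with a cross-reference to SAP 2.1.
3. State in advance how receipt of the assigned procedure is derived from the recorded infusion rate, infusion and ultrasound durations, termination reason and deviation flag. Include how subjects with a discontinued infusion, or with infusion but no ultrasound, are classified for analysis.
4. Apply the same flag to the original-study subjects in the pooled analysis.
5. Report exclusions per arm with reasons. Leave ITT unchanged and read the evaluable result beside it.

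Cost: SAP wording and a derived flag from data already tabulated for the UK subjects. Items 9 and 10 carry no asterisk for the combined analysis, so deriving the flag for the original study is extra work. The evaluable n will be smaller, and post-randomisation exclusions may introduce selection.

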10.2 General Methodology

Unless otherwise specified, all analysis will be performed separately for each of the treatment arms and separately for unilateral and bilateral patients within each treatment arm. For Screening/Baseline demographics and subject or disease characteristics, continuous measures will be summarized as mean, standard deviation, median, minimum and maximum. Categorical data will be summarized as frequencies and percentages for each data category. For changes from Screening/Baseline to follow-up time points, continuous measures will be summarized as mean, standard deviation, median, minimum, and maximum. Categorical outcomes will be summarized in two-way tables. Statistical significance for changes from Screening/Baseline will be assessed by t-test or a nonparametric test as appropriate for continuous data; Fisher's exact test will be done for 2x2 tables and Friedman Halton exact test will be performed for tables with higher dimensions.

Further analysis details will be described in the Statistical Analysis Plan.

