2.2 General Methodology

All analyses will be performed separately for each of the treatment arms. Continuous measures will be summarized as n, mean, standard deviation, median, minimum and maximum. Categorical data will be summarized as frequency and percentage for each data category.

Where possible and indicated in Appendix 1 List of Tables , a pooled analysis will be performed with the OPTALYSE PE and OPTALYSE UK extension data combined. In each case, the same Analysis Subject Set for each population will be used.

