2.5 Sample Size And Power Estimation

The primary efficacy endpoint for the study is the 48-hour decrease in RV/LV ratio. The Fasullo¹ study's heparin arm indicated a mean RV/LV ratio decrease of 0.20. Based on these results, we propose a mean

48-hour RV/LV ratio (absolute) decrease ≤ 0.20 as the null hypothesis for this study. Rejecting the null hypothesis with a 1-sided $p<0.15$ by t test will be regarded as a positive sign for further investigating a treatment regimen. For submassive PE subjects in the SEATTLE II study, a mean RV/LV ratio reduction of 0.43 was observed with a standard deviation of 0.41. Should these results be true for a regimen in the current study, with 25 evaluable subjects, the power to detect a positive signal is approximately 0.96.

The simultaneous power for the three treatment groups at the planned sample size of with $n=25$ evaluable per arm is approximately 0.88 by the Hochberg procedure².

Appendix 1: List of Tables (All summaries and analyses will be by treatment arm for the UK Extension portion of the study unless otherwise specified. Except for RV/LV ratio analyses, all p values are 2-sided. Analyses that will be conducted for the combined portions of the study (OPTALYSE PE plus UK Extension) as well as for the UK Extension alone and are indicated by an asterisk.)

Subject Set = ITT for (1) – (20) Unless Otherwise Specified

- 1) Enrollment by Site
- 2) Demographics
 - a) Age
 - b) Weight
 - c) BMI
 - d) Gender
 - e) Ethnicity (Hispanic vs. not Hispanic)
 - f) Race
- 3) Clinical History and Risk Factors
 - (a) – (v) on *Clinical History and Risk Factors CRF*.
 - a) Hypercholesterolemia
 - b) Congestive Heart Failure
 - c) Hepatic Insufficiency
 - d) Renal Insufficiency
 - e) TIA or Stroke
 - f) Active Cancer
 - g) Diabetes
 - h) Hypertension
 - i) Tobacco use
 - j) $BMI \geq 30.0$
 - k) COPD
 - l) History of Cancer in Remission
 - m) Family History of VTE
 - n) Chronic Inflammatory Disorders
 - o) Acute Infectious Illness within 30 Days of signing ICF
 - p) Atherosclerotic Cardiovascular Disease
 - q) Currently taking a Hormonal Contraceptive or Replacement Therapy
 - r) Osteoarthritis of Either Hip or Knee

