At screening/Baseline, start and end of the APT procedure, within 4 hours of end of APT procedure and 24 hours, 48 hours, 30 days, 90 days, and 365 days after the start of the APT procedure:

- a) Systolic BP
- b) Diastolic BP
- c) Heart Rate
- d) Respiratory Rate
- e) SpO2
- f) Oxygen Source

For each of (a) through (e), summarize as n, mean, standard deviation, median, minimum, maximum at each time point; construct box/whiskers plots for all 7 timepoints in the same graph and connect means and medians. For (f), summarize as frequency and percent in the order of room air, nasal prongs, mask and intubated at each time point

6.2) Laboratory Data

- a) Hemoglobin
- b) Hematocrit
- c) Platelet
- d) aPTT
- e) PT

- f) INR
- g) Troponin
- h) D-dimer
- i) BNP/proBNP
- j) Lactate/Lactic Acid

For each of (a) through (f), summarize as n, mean, standard deviation, median, minimum, maximum at baseline, post procedure 1 (within 4 hours post treatment) and post procedure 2 (48 hours).

For (g) through (j), summarize as n, mean, standard deviation, median, minimum, maximum at baseline and post procedure (48 hours).

6.3) PESI/sPESI

Summarize as n, mean, standard deviation, median, minimum, maximum at baseline, post procedure 1 (within 4 hours post treatment), post procedure 2 (24 hours) and post procedure 3 (48 hours).

7) Interventional Procedure

- a) Access Site Location
- b) Ultrasound Imaging Used
- c) Number of Attempts Required to Gain Access
- d) Total r-tPA dose per patient

8) EkoSonic Device Information

- a) Number of Devices Successfully Placed and Used for Treatment per Patient (*table entries are numbers of patients*) (*A footnote will be added with total # devices which were not "successfully placed and used for treatment" with reasons.*)
- b) EkoSonic Device Placement Site (*table entries are numbers of devices*)

9) Thrombolytic Infusion Details (by device used)

- a) r-tPA concentration (mg/mL)
- b) r-tPA infusion rate (mg/hr)
- c) Duration of r-tPA infusion (hrs)
- d) Reason for Infusion termination (completed per protocol, AE, or other)
- e) Deviations from prescribed therapy and reason (Protocol Deviation CRF, include all deviations with “APT Procedure not Performed as Prescribed by Protocol” checked)

10) EkoSonic System Details

- a) Duration of Ultrasound (hrs)
- b) Reason for ultrasound termination
- c) Deviations from prescribed therapy and reason

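### The SAP's safety sections and tables leave assigned versus received treatment undefined and do not split bleeding by catheter number or r-tPA dose given, contrary to protocol 10.1 and the SAP's own synopsis

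*SAP*

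**What the plan says.** **Protocol.** Section 10.1 gives an unqualified rule for safety: "Safety analysis will be performed on the Safety Evaluable Subject Set according to the actual treatment received". Section 10.2 says that "all analysis will be performed separately for each of the treatment arms and separately for unilateral and bilateral patients within each treatment arm". That sentence opens with a proviso allowing other specification, and the section leaves further detail to the SAP.

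**SAP text.** Section 2.1 defines the Safety Subject Set by whether venous access for the catheter was attempted, and says that it "includes all safety evaluable subjects and will be used for all safety analyses". It does not say whether those subjects are tabulated by assigned or received regimen. Section 2.2 reads "All analyses will be performed separately for each of the treatment arms", without the unilateral/bilateral clause. Section 2.4 specifies the major-bleeding proportion with a Wilson interval and adds no grouping rule.

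**SAP Appendix 1.** The header sets the default: "All summaries and analyses will be by treatment arm for the UK Extension portion of the study unless otherwise specified". The Safety Subject Set tables (major bleeding, the second item numbered 21; bleeding events, item 25(f)) specify no other grouping. The six-way split is spelled out in item 11, the CTA RV/LV table: "repeat the above analyses for ITT patients as 6 arms, i.e. unilateral vs. bilateral for each of the 3 randomization arms". Dose given appears as item 7(d), "Total r-tPA dose per patient", a stand-alone ITT table.

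**SAP synopsis.** The note under Treatment Arms says: "All data will be summarized by total r-tPA dose administered, i.e. six groups".

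**The concern.** The objective is the optimum r-tPA dose and procedure duration, and the primary safety outcome is major bleeding within 72 hours. A reader has to be able to set bleeding against the dose and regimen given, and the listed safety tables do not provide for this.

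First, a programmer cannot tell from the SAP which arm a subject belongs to when delivery departed from assignment. Such departures are foreseen. Protocol 6.3.4 lists events that end the procedure, protocol 6.6 asks for rate and dose again if the procedure is restarted, and protocol 8.5.2 allows infusion to continue without ultrasound after a malfunction. The access-attempted definition also admits subjects who never received r-tPA, and no table row is provided for them.

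Second, if the listed tables are followed, one-catheter and two-catheter patients share a row although their planned doses differ by a factor of two. The major-bleeding table is marked for pooling with OPTALYSE PE, so both gaps carry into the pooled result.

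**Working it through.** **1. Dose table.** Inputs: duration and rate per catheter from the Treatment Arms table (the same in both documents). Total dose = hours × mg/h/catheter × catheters.

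| Group | One catheter | Two catheters |
|---|---|---|
| 1 | 2 × 2 × 1 = 4 mg | 2 × 2 × 2 = 8 mg |
| 2 | 4 × 1 × 1 = 4 mg | 4 × 1 × 2 = 8 mg |
| 3 | 6 × 1 × 1 = 6 mg | 6 × 1 × 2 = 12 mg |

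This reproduces the stated 4/8, 4/8 and 6/12 mg. The distinct totals are 4, 6, 8 and 12 mg, which is four levels. Six groups come only from 3 arms × 2 catheter numbers. A table by total dose and a table in six groups are therefore different tables, and the synopsis note equates them.

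**2. Rule by rule.**

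| Rule | Protocol | SAP methods (2.1, 2.2, 2.4) | SAP safety tables | SAP synopsis |
|---|---|---|---|---|
| Safety by treatment received | Yes (10.1) | Not stated | Not stated | Dose administered, all data |
| One versus two catheters | Yes, unless otherwise specified (10.2) | Arm only (2.2) | Arm only, by default | Six groups, all data |

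**3. Mixing of doses within an arm.** Let u be the unilateral share. Mean planned dose = D × (1 − u/2), where D is the two-catheter dose. The documents do not give u. Protocol section 4 anticipates 30 enrolled per arm for 25 bilaterally treated evaluable subjects, so 5/30 = 16.7% serves as an illustration. The range 0 to 25% is an assumption.

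| u | Groups 1 and 2 | Group 3 |
|---|---|---|
| 0 | 8.0 mg | 12.0 mg |
| 5/30 | 8 × (1 − 1/12) = 7.33 mg | 12 × (1 − 1/12) = 11.0 mg |
| 25% | 8 × 0.875 = 7.0 mg | 12 × 0.875 = 10.5 mg |

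**4. Sensitivity of an arm row to where one subject is counted.** The SAP synopsis gives 29 UK subjects. With an even split (assumed), 29/3 ≈ 9.7, or about 10 per arm. For zero events the Wilson upper limit is z²/(n + z²), with z² = 3.84.

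- 1/10 = 10%, 95% Wilson interval 1.8% to 40.4%.
- 0/10: 3.84/13.84 = 27.8%, so 0 to 27.8%.
- If one subject with a bleed moves between two arms of 10, the subject leaves one denominator and joins the other. The arm losing the subject goes from 1/10 to 0/9 (0 to 3.84/12.84 = 29.9%). The arm gaining the subject goes from 0/10 to 1/11 = 9.1% (1.6% to 37.7%).

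The documents give no rate of delivery in the wrong regimen, so this shows sensitivity and does not predict an error.

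**5. Cell size after a split.** At 16.7%, an arm of 9.7 has about 1.6 one-catheter subjects, or about 2. For 0/2 the interval is 0 to 3.84/5.84 = 65.8%.

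**The case against.** Much of the opposing case stands, and it limits the point to the safety tables.

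- **A reader might infer that the SAP assigns safety events to the randomised regimen.** It does not say so. SAP 2.2 and the Appendix 1 header speak only of treatment arms, and the phrase about randomisation arms belongs to an ITT efficacy table. Nothing in the SAP contradicts protocol 10.1. The rule is missing, not replaced.
- **A reader might infer that the SAP has abandoned dose grouping.** The synopsis still requires it for all data. The methods and safety tables fail to carry out that statement, which is a conflict within the SAP.
- **A reader might infer that the six-way split survives only for CTA RV/LV.** The echocardiographic items in Appendix 1 ask for the same analysis as item 11, with listed exceptions that do not include the six-arm repeat, so the split is arguably inherited there. The unilateral/bilateral indicator is also a covariate in the trend regression and the repeated-measures model. The gap is in safety.
- **Protocol 10.2 permits departure.** Its proviso means that the missing catheter split is not by itself a breach of the protocol. The firmer conflicts are with protocol 10.1 and with the SAP synopsis.
- **The inputs are tabulated.** Dose, devices used, infusion rate and duration, and deviations appear in Appendix 1 items 7 to 10, and bleeding judged related to the thrombolytic is in item 25(f). This is true, but none of these is crossed with bleeding.
- **A reader might say that the two-catheter bleeding rate is diluted.** That presumes that bleeding rises with dose. Under protocol 6.3.4 the number of catheters follows clot distribution, so one- and two-catheter patients may differ in other ways.

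**Conclusion.** The point holds for SAP 2.1, 2.2, 2.4 and the Safety Subject Set tables. Whether safety is tabulated by assigned or received regimen is undefined, and the bleeding tables do not carry out the dose grouping that the synopsis promises. Following the listed tables would report bleeding for arms that mix planned doses differing two-fold. The dose arithmetic is exact.

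The practical effect cannot be sized from the documents, because they state neither the unilateral share nor any rate of departure from assignment. The 17% is a planning allowance that also covers other reasons for being non-evaluable. It is tempting to read it as an upper bound, but protocol section 4 allows additional subjects to be consented to compensate for one-catheter treatment, so the true share could be higher or lower. The figures for arms of 10 assume an even split of the 29 UK subjects.

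This is a worthwhile and inexpensive correction to descriptive safety reporting. It does not touch the primary efficacy test or the sample size.

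**What to change.** 1. In SAP 2.1 and 2.4, state that Safety Subject Set tables are by regimen actually received, determined from the delivered rate and duration (Appendix 1 items 9 and 10). Name the row for subjects with access attempted but no r-tPA, and say how partial and restarted infusions are classified.
2. For the Safety Subject Set major-bleeding table (the second item numbered 21; the first is protocol deviations) and for item 25(f), add one descriptive display by arm and number of catheters used (item 8(a)) and one by delivered total r-tPA (item 7(d)). Produce them for the UK data, and for the pooled data where the table carries the pooling asterisk, which the major-bleeding table does.
3. Reword the synopsis note as six groups defined by arm and number of catheters used.

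The cost is SAP wording and a few descriptive displays from data already collected. The downside is sparse cells: with 29 UK subjects a one-catheter cell may hold about two people. Footnote the displays as descriptive, and state that the catheter split is not a randomised dose comparison.
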